5.5 Criteria for Subject Withdrawal

5.5.1 Withdrawal from the Trial

Subjects are free to discontinue the trial at any time without giving their reasons.

A subject must be withdrawn in the event of any of the following:

Withdrawal of the subject's consent.

Participation in any other interventional trial during the duration of this trial

Withdrawal of the Investigational Medicinal Product

If a subject has failed to attend scheduled trial assessments, the Investigator must determine and record the reasons and the circumstances as completely and accurately as possible.

In any case, the appropriate Case Report Form (CRF) section must be completed.

5.5.2 Withdrawal from the Investigational Medicinal Product

The subject must be withdrawn in the event of any of the following:

Occurrence of an exclusion criterion which is clinically relevant and affects the subject's safety, if discontinuation is considered necessary by the Investigator and/or Sponsor.

Therapeutic failure requiring urgent additional drug, or dose adjustment of other anti-angina drugs that investigator believes would affect the function/perfusion of coronary microvascular, including but not limited to ACEI, ARB, Statins, β -blockers, CCB,

ivabradine, and trimetazidine, also other long-term Chinese traditional medicines for the treatment of angina.

Occurrence of adverse events, if discontinuation of trial drug is desired or considered necessary by the Investigator and/or the subject.

Occurrence of pregnancy.

Use of a non-permitted concomitant drug, as defined in Section 6.5.2, where the predefined consequence is withdrawal from the IMP.

Non-compliance.

5.6 Premature Discontinuation of the Trial

The whole trial may be discontinued prematurely in the event of any of the following:

New information leading to unfavorable risk-benefit judgment of the IMP, e.g. due to:

Evidence of inefficacy of the IMP,

Occurrence of significant previously unknown adverse reactions or unexpectedly high intensity or incidence of known adverse reactions, or

Other unfavorable safety findings.

(Note: evidence of inefficacy may arise from this trial or from other trials; unfavorable safety findings may arise from clinical or non-clinical examinations, e.g. toxicology.)

Sponsor's decision that continuation of the trial is unjustifiable for medical or ethical reasons.

Poor enrollment of subjects making completion of the trial within an acceptable time frame unlikely.

Discontinuation of development of the Sponsor's IMP.

Withdrawal of the IMP from the market for safety reasons (applicable to trials with marketed products only).

Ethics Committee and Institutional Review Boards (IRBs) will be informed about the discontinuation of the trial in accordance with applicable regulations.

The whole trial may be terminated or suspended upon request of Health Authorities.

6 Investigational Medicinal Product and Other Drugs Used in the Trial

The term "Investigational Medicinal Product" refers to the investigational drug undergoing trial.

6.1 Description of Investigational Medicinal Product

Nicorandil (Sigmart® Tablets, 5mg), white plain tablets, with diameter 5mm, thickness 2mm, manufactured by PPD .

6.2 Dosage and Administration

During the whole study duration, subjects in nicorandil group would take Sigmart® orally, 5mg, t.i.d. The whole tablet is to be swallowed with water, not chewed.

Treatment of angina pectoris:

The usual adult dosage for oral use is 15 mg of nicorandil daily in three divided doses. The dosage may be adjusted according to the patient's condition.

In this study, according to the small sample size, single-arm design for primary endpoint, and the usual dose of Sigmart® in China, the dose is required not to change during the study duration.

6.3 Assignment to Treatment Groups

After completion of all the screening evaluations, 20 eligible subjects will be enroll to treatment group.

Subject numbers should be unique (i.e. reallocation of subject numbers is not permitted).

6.4 Other Drugs to be used in the Trial

No other drugs are mandatory in this trial.

For nicorandil group, all other long acting cardiovascular disease medicines, including aspirin/clopidogrel, CCB, ACEI/ARB, β -blockers, statins, ivabradine, trimetazidine, et al, should be stable taken for at least one month before screening period;

For standard treatment group, the standard treatment should include aspirin/clopidogrel, CCB, ACEI/ARB, β -blockers and statins if condition permits. They should also be taken for at least one month before screening period.

6.5 Concomitant Medications and Therapies

6.5.1 Permitted Medicines

Any medications (other than those excluded by the clinical trial protocol) that are considered necessary for the subjects' welfare and will not interfere with the trial medication may be given at the Investigator's discretion.

Patients should take all the current standard therapy for angina. It should include aspirine / clopidogrel, ACEI/ARB, statins, β -blockers and CCBs. Other medicines for angina treatment are also permitted, such as ivabradine, trimetazidine, and other Chinese traditional medicines, such as Tong Xin Luo capsule. However, all these medicines mentioned in this paragraph need to be stabilized before screening period. There should be no dose/form change during the trial.

Emergency medicines for sudden angina attacks such as nitroglycerin and Compound Danshen Dripping Pills, are permitted in the trial duration. Their usage is not restricted. But the dose and frequency should be recorded in the corresponding section of the CRF at every visit.

The Investigator will record all concomitant medications taken by the subject during the trial, from the date of signature of informed consent, in the appropriate section of the CRF.

Any additional concomitant therapy that becomes necessary during the trial and any change to concomitant drugs must be recorded in the corresponding section of the CRF, noting the name, dose, duration and indication of each drug.

6.5.2 Non-permitted Medicines

Glyburide, which may influence the efficacy of nicorandil;

PDE-5 inhibitors, such as sildenafil citrate, vardenafil hydrochloride hydrate and tadalafil. The coadministration of these medicines with nicorandil may enhance hypotensive effect;

Soluble guanylate cyclase stimulator(s), such as riociguat. The co-administration with nicorandil may enhance hypotensive effect.

Some evidences showed that ranolazine could effect coronary microvascular function. So it should not be used during the study period and one month before the screening period.

Some injections that might have efficacy on patients' microvascular function are also not permitted during the study, such as alprostadil injection.

Any other additional concomitant therapy that becomes necessary during the trial and any change to concomitant drugs must be recorded in the corresponding section of the CRF, noting the name, dose, duration and indication of each drug.

If the administration of a non-permitted concomitant drug becomes necessary during the trial, e.g., because of AEs, the subject should withdraw from the study, the data should only be used for safety

6.5.3 Other Trial Considerations

If the subjects undergone PCI or CABG during the study, they should withdraw from the trial. If patients need to perform other surgeries that need hospitalization, they should withdraw from the trial.

6.5.4 Special Precautions

- (1) For drugs that are dispensed in a press-through package (PTP), instruct the patient to remove the drug from the package prior to use. (It has been reported that, if the PTP sheet is accidentally swallowed, the sharp corners of the sheet may puncture the esophageal mucosa, resulting in perforation, and possible severe complications such as mediastinitis);
- (2) Instruct the patient to avoid moisture and to keep the medicine in a cool place;
- (3) Keep out of children;
- (4) Expired drug should not be used.

6.6 Packaging and Labeling

Packaging: 5mg tablets, boxes of 100 tablets in PTP. One box would supply for 33 days.

Labeling: “use only for clinical study EMR200505_506” will be labelled on the box by an independent company.

Packaging and labeling will be in accordance with applicable local regulatory requirements and applicable GMP Guidelines.

6.7 Preparation, Handling and Storage

Nicorandil is freely soluble in methanol, ethanol (99.5), acetic acid (100); soluble in acetic anhydride; sparingly soluble in water. The melting point is about 92°C (to be decomposed). So the medicine should be stored in room temperature and avoid moisture.

6.8 Investigational Medicinal Product Accountability

The Storage Manager at the trial site who was assigned by the Head of the trial site is responsible for ensuring accountability for the IMP, including reconciliation of drugs and maintenance of drug records.

After the conclusion of the trial contract with the trial site, the Sponsor (or designee) may deliver the IMP to the Storage Manager at the trial site.

Upon receipt of the IMP, the Storage Manager will check for accurate delivery and acknowledge receipt by signing and dating the documentation provided by the Sponsor and returning it to the Sponsor. A copy will be archived in the Investigator Site File.

The dispensing of the IMP will be carefully recorded by the Storage Manager on the appropriate drug accountability forms provided by the Sponsor so that accurate records will be available for verification by the Sponsor Monitor at each monitoring visit.

IMP accountability records will include the following:

Confirmation of IMP delivery to/receipt by the trial site.

IMP accountability forms (provided by the Sponsor and completed at the site).

The use of each dose by each subject.

The return to the Sponsor or alternative disposition of unused IMP.

Dates, quantities, batch numbers, expiry dates, formulation (for IMP prepared at the site), and the subjects' trial numbers.

The Storage Manager should maintain records that adequately document the following:

The subjects received the doses specified by the clinical trial protocol/amendment(s);
and

All IMPs provided by the Sponsor were fully reconciled.

The unused IMP must not be discarded or used for any purpose other than the present trial. IMP that has been dispensed to a subject must not be re-dispensed to a different subject.

The Sponsor Monitor will periodically collect the IMP accountability forms and will check all the IMPs to be returned or discarded before arrangements for returns (both unused and used containers) are made at the trial site or their destruction by the trial site is authorized.

6.9 Assessment of Investigational Medicinal Product Compliance

Subjects should be instructed to bring with them to each visit both opened and unopened IMP packages, in order to allow the assessment of compliance with trial treatment. IMP administration must be recorded in the CRF, as applicable.

Medication possession ratio (MPR) is used to assess the medicine compliance. MPR is defined as the actual drug number taken by the patients divided by the drug number should be taken by the patients according to the protocol. MPR between 80%-100% is defined as good compliance. Medication rate of <80% or >100% is defined as insufficient compliance.

6.10 Method of Blinding

NA

6.11 Emergency Unblinding

NA

6.12 Treatment of Overdose

An overdose is defined as any dose greater than the highest daily dose included in the clinical trial protocol. Any overdose must be recorded in the trial medication section of the CRF.

For monitoring purposes, any case of overdose – whether or not associated with an adverse event (serious or non-serious) – must be reported to the Sponsor's Global Drug Safety department in an expedited manner using the appropriate reporting form (see Section 7.4.1.4).

The usual adult dosage for oral use is 15 mg of nicorandil daily in three divided doses. The dosage may be adjusted according to the patient's condition. Till now, there is no maximum dose for nicorandil. In a clinical trial conducted in European stable angina patients, the dose of nicorandil was 20mg, twice daily with a mean follow up of 1.6 years. Patients showed good tolerance of the medicine and less coronary events ^[25].

If patients took more dose of nicorandil than 15mg/d, the investigators should use his/her clinical judgement treating such situations.

6.13 Medical Care of Subjects after End of Trial

After a subject has completed the trial or has withdrawn early, usual treatment will be administered, if required, in accordance with the trial site's standard of care and generally accepted medical practice and depending on the subject's individual medical needs.

7 Trial Procedures and Assessments

7.1 Schedule of Assessments

Day 1 is defined as the first day of enrollment.

The trial procedures and assessment contents are as follow:

1. Screening Visit -Day -14 to 0: this visit entails the following:

Before any procedures that are related to the trial is undertaken, informed consent of the patient should be obtained. Thereafter, basic information of the patient will be obtained and patients are screened for eligibility based on the inclusion and exclusion criteria.

- a) Record birth date, gender, height, weight, waist circumference, current medical condition and past medical history, including concomitant therapies
- b) Perform physical examinations, including vital signs (blood pressure, heart rate)
- c) ECG: heart rate; sinus rhythm/arrhythmia, specify; cardiac hypertrophy(yes/no); abnormal ST-T change(yes/no),if yes, specify;
- d) Echocardiography
- e) Rest and stress PET
- f) Blood tests: full blood count (white blood cells, neutrophils, red blood cells, hemoglobin and platelets), myocardial enzymes(CKMB), liver function (ALT, AST), renal function (Bun, Cr), fasting blood glucose and blood lipids (TC, TG, LDL-C and HDL-C), electrolyte (K, Na) (data within -28 days of liver function, renal function, fasting blood glucose and blood lipids are accepted)
- g) Routine urine test (PH, Specific gravity, Protein, Glucose, Ketone, Nitrite, Leukocytes, Hemoglobin, Red blood cells, Bilirubin), urine pregnancy test
- h) Signing the informed consent form
- i) AE
- j) Concomitant medication

2. Visit 1- Day 1±3: this visit entails the following:

- a) Enrollment.
- b) Perform physical examinations, including vital signs (blood pressure, heart rate)
- c) ECG: heart rate; sinus rhythm/arrhythmia, specify; cardiac hypertrophy(yes/no); abnormal ST-T change(yes/no),if yes, specify;
- d) Seattle Angina Questionnaire score;

- e) Cardiovascular events: cardiac death, hospitalization caused by heart failure/ACS/revascularization, stroke, cerebral hemorrhage;
- f) AE;
- g) Concomitant medication

3. Visit 2- Day 28±3: This visit entails the following:

- a) Perform physical examinations, including vital signs (blood pressure, heart rate
- b) ECG: heart rate; sinus rhythm/arrhythmia, specify; cardiac hypertrophy(yes/no); abnormal ST-T change(yes/no),if yes, specify;
- c) Record adverse events, concomitant drugs and use of study drug;
- d) Cardiovascular events: cardiac death, hospitalization caused by heart failure/ACS/revascularization, stroke, cerebral hemorrhage;

4. Visit 3- Day 56±3: This visit entails the following:

- a) Perform physical examinations, including vital signs (blood pressure, heart rate)
- b) ECG: heart rate; sinus rhythm/arrhythmia, specify; cardiac hypertrophy(yes/no); abnormal ST-T change(yes/no), if yes, specify;
- c) Record adverse events, concomitant drugs and use of study drug;
- d) Cardiovascular events: cardiac death, hospitalization caused by heart failure/ACS/revascularization, stroke, cerebral hemorrhage;

5. Visit 4- Day 84±3: This visit entails the following:

- a) Record height, weight and waist circumference
- b) Perform physical examinations, including vital signs (blood pressure, heart rate)
- c) ECG: heart rate; sinus rhythm/arrhythmia, specify; cardiac hypertrophy (yes/no); abnormal ST-T change(yes/no), if yes, specify;
- d) Echocardiography
- e) Rest and stress PET
- f) Seattle Angina Questionnaire score
- g) Blood tests: full blood count (white blood cells, neutrophils, red blood cells, hemoglobin and platelets), myocardial enzymes (CKMB), liver function (ALT, AST), renal function (Bun, Cr), fasting blood glucose and blood lipids (TC, TG, LDL-C and HDL-C), electrolyte (K, Na)

h) Routine urine test (PH, Specific gravity, Protein, Glucose, Ketone, Nitrite, Leukocytes, Hemoglobin, Red blood cells, Bilirubin);

i) Record adverse events, concomitant drugs and use of study drug;

j) Cardiovascular events: cardiac death, hospitalization caused by heart failure/ACS/revascularization, stroke, cerebral hemorrhage;

k) Compliance; Prior to performing any trial assessments not part of the subject's routine medical care, the Investigator will ensure that the subject or the subject's legal representative has provided written informed consent according to the procedure described in Section 9.2.

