UCG	Ultrasound Cardiogram

Trial title	An interventional, pilot study to evaluate the efficacy of oral nicorandil on improving microvascular function in female non-obstructive CAD patients (SPET study)
Trial number	EMR200505-506
Sponsor	Merck Serono Co., Ltd
Phase	IV
Trial center(s)/country(ies)	1(hospital)/1(country)
Planned trial period (first enrollment-last subject out)	Sep, 2016 - Oct, 2019
Trial objectives	
Primary objective:
 
To evaluate the improvement of microvascular function by positron emission tomography (PET) after twelve-week treatment of oral nicorandil in female no obstructive CAD patients;
 
Secondary objectives:
 
1) To evaluate the improve of myocardial blood flow (MBF) by rest and stress PET after twelve-week treatment of oral nicorandil
 
2)To evaluate the improve of heart function by echocardiography after twelve-week treatment of oral nicorandil
 
3) To evaluate the improve of angina attacks after twelve-week treatment of oral nicorandil

s	This is a single-center, interventional, pilot clinical trial. 11-20 patients will be enrolled in the treatment group who will take oral nicorandil 5mg, t.i.d for 12 weeks,. For all the patients, rest cardiac PET and stress cardiac PET will be tested at both screening period and end of study. Other laboratory parameters and clinical symptoms will be collected at baseline, 4 weeks, 8 weeks and 12 weeks of treatment. There will be 5 visits from the beginning to the end of the study

Planned number of subjects	11-20
Schedule of visits and assessments	
Screening visit: ECG, lab tests, MFR by rest and stress PET, UCG;
 
Visit 1(week 0): ECG, SAQ;
 
Visit 2 (week 4): ECG;
 
Visit 3 (week 8): ECG;
 
Visit 4 (week 12): ECG, lab tests, MFR by rest and stress PET, UCG

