5.1.1 Major aspects of the trial

There will be a 2-week screening period, when baseline lab tests, ECG, UCG and PET will be conducted in this period. Patients who met the inclusion criteria but not the exclusion criteria will be enrolled. Totally 11-20 patients will be enrolled in the study. The study period after enrollment is 12 weeks. The anticipated recruitment period is 12 months. The anticipated period of the whole study will be 15 months. According to the recruitment

[figure not shown]
progress, if there have been 11 patients complete their following period, this study could be accomplished when meet the end of the anticipated period of the whole study.

Patients in the nicorandil group will start to take nicorandil 5mg, t.i.d from visit 1 for 12 weeks. All other cardiovascular medicines which need to be stabilized at least two weeks before screening period will be continued. Patients in standard treatment group will still take all the cardiovascular medicines stabilized at least two weeks before screening without any other newly added drugs. There will be a visit every four weeks. Symptoms and safety issues will be assessed at visit 2, visit 3. At visit 4 (week 12, end of treatment), lab tests, ECG, UCG, PET, symptoms and safety issues will all be re-assessed.

The primary endpoint is the MFR tested by PET at baseline and end of treatment; the secondary endpoints include the MBF by rest and stress PET at baseline and end of treatment, the heart function at baseline and end of treatment (based on UCG), symptom and quality of life at baseline and end of treatment (based on Seattle Angina Questionnaire).

In order to collect all the information in the inclusion and exclusion criteria for subjects' enrollment, medical history, physical examination, lab tests, ECG and UCG should be conducted in a 2-week screening period. As MFR by PET is also an inclusion criteria, rest and stress PET should also be conducted in subjects who have already met all other inclusion but not exclusion criteria in this 2-week screening period. If patients conducted lab tests, ECG or UCG in this period, but not especially for this trial, the result could also be used for the screening. 20 patients who meet the inclusion criteria but not the exclusion criteria will be enrolled in the study.

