5.4 Criteria for Initiation of Treatment with the Investigational Medicinal Product

The inclusion and exclusion criteria examined at screening shouldn't be checked again before initiation of the treatment.

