7.2.4 Lab test items

Lab examination should include at least the following items: hematological examination, echocardiography, rest and stress PET need to be done at the screening visit and last visit; ECG need to be done at every visit.

1. Hematology tests (all these lab test need to be done by fast in the morning):

a) Full blood count: red blood cell count, neutrophils, hemoglobin, white blood cell count and platelet count

b) Liver function (ALT, AST)

c) Kidney function (BUN, Cr)

d) Fasting blood glucose

e) Blood lipid levels (TC, TG, HDL-C, LDL-C)

f) Myocardial enzymes (CKMB)

g) Electrolyte (K, Na)

2. Routine urine test (PH, Specific gravity, Protein, Glucose, Ketone, Nitrite, Leukocytes, Hemoglobin, Red blood cells, Bilirubin), urine pregnancy test

3. ECG: heart rate; sinus rhythm/arrhythmia, depict what kind of arrhythmia; cardiac hypertrophy (yes/no); abnormal ST-T change (yes/no);

4. Echocardiography: to measure ejection fraction (EF%), left ventricular end systolic diameter (LVESD), interventricular septum thickness (IVST), left ventricular posterior wall thickness (PWT) and E/A ratio

5. Rest and stress PET: MBF of both rest and stress PET, then $MFR = MBF \text{ at stress} / MBF \text{ at rest}$ (the detailed description of PET test will be described in 7.3.1)

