7.4.3 Laboratory Assessments

All laboratory assessments have been detailed listed in Section 7.1 and Section 7.2.

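### Section 7.1 lists a urine pregnancy test with the first PET but not with the repeat PET at Visit 4, when the last scheduled result is 81 to 101 days old

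*Protocol*

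**What the plan says.** Protocol 7.1 is the visit-by-visit list. At screening (Day -14 to 0) it has rest and stress PET as item e), and urine testing as item g), which ends "Leukocytes, Hemoglobin, Red blood cells, Bilirubin), urine pregnancy test". At Visit 4 (Day 84±3) rest and stress PET is again item e), and urine testing is item h): "h) Routine urine test (PH, Specific gravity, Protein, Glucose, Ketone, Nitrite, Leukocytes, Hemoglobin, Red blood cells, Bilirubin". The panel closes there, with no pregnancy test after it. Visits 1, 2 and 3 list no urine or pregnancy test. Appendix I has no row for either.

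On the order of events at screening, 5.1.1 reserves the PET for use "in subjects who have already met all other inclusion but not exclusion criteria in this 2-week screening period". Pregnancy, and child-bearing potential without effective contraception, are exclusion 15 in 5.3.2. For the start of treatment, 5.4 adds: "The inclusion and exclusion criteria examined at screening shouldn't be checked again before initiation of the treatment".

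Elsewhere the protocol is less specific:

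- The synopsis has "Visit 4 (week 12): ECG, lab tests, MFR by rest and stress PET, UCG".
- Section 5.1.1 says of the same visit that "lab tests, ECG, UCG, PET, symptoms and safety issues will all be re-assessed".
- Section 7.2.4 includes the urine pregnancy test in its minimum list of laboratory items but attaches no visit to it. Its timing sentence reads "hematological examination, echocardiography, rest and stress PET need to be done at the screening visit and last visit".
- Section 7.4.3 says "All laboratory assessments have been detailed listed in Section 7.1 and Section 7.2".

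**The concern.** Both PET sessions follow the same procedure: two injections of N-13 ammonia and a low-dose CT for attenuation correction (7.3.1). Before the first, the eligibility sequence means pregnancy has been excluded by a test. Before the second, a site working from 7.1 has no test result more recent than screening. The urine panel is otherwise identical at the two visits, so the pregnancy test is the only urine item dropped, and the protocol gives no reason.

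What is at stake is participant safety. A woman who conceives during the twelve weeks of treatment and has not recognised it would receive the second tracer and CT exposure unchecked. The risk-benefit section (3.2) discusses radiation dose but not pregnancy. The MFR comparison, its paired t test and the sample size do not depend on this point.

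**Working it through.** The protocol states no figure for the age of the pregnancy test at the second PET, so there is nothing to reproduce. The interval follows from the visit windows.

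**Inputs**

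- Screening window, for the test and the first PET: Day -14 to Day 0 (7.1).
- Visit 4 window, for the second PET: Day 84±3, that is Day 81 to Day 87 (7.1).
- Tracer: 370 to 740 MBq per injection, one at rest and one at stress (7.3.1).
- Dose factor: 1.5 mSv per 10 mCi of N-13 ammonia (3.2).

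**Age of the last scheduled test at each PET**

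| PET | Shortest gap | Longest gap |
|---|---|---|
| First (screening) | same day = 0 days | 0 - (-14) = 14 days |
| Second (Visit 4) | 81 - 0 = 81 days | 87 - (-14) = 101 days |

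At the nominal Day 84 the second gap is 84 - 0 = 84 to 84 - (-14) = 98 days.

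**Visits after screening at which 7.1 lists the test:** Visit 1 no, Visit 2 no, Visit 3 no, Visit 4 no, so 0 of 4. Only Visit 4 has a PET.

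**Maternal tracer dose at the second PET**

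- 370/37 = 10 mCi and 740/37 = 20 mCi per injection, which agrees with the 10 to 20 mCi in 3.2.
- Low end: 2 × 10 mCi × 1.5 mSv / 10 mCi = 3.0 mSv.
- High end: 2 × 20 mCi × 1.5 mSv / 10 mCi = 6.0 mSv.
- The CT comes on top; its dose is not stated. No fetal dose is given.

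**Does any other text require the test at Visit 4?** The timing sentence in 7.2.4 names blood tests, echocardiography and PET for the screening and last visits; it does not name urine or pregnancy tests. The synopsis and 5.1.1 refer only to laboratory tests in general. Section 7.4.3 points to 7.1 and 7.2 together and does not say which governs. None of these schedules the test at Visit 4, and the one section that itemises each visit omits it.

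**After the fix:** with a test and PET both inside Day 81 to 87, the result is 0 to 87 - 81 = 6 days old.

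**The case against.** The best counter-argument is that the test may already be due at Visit 4. Section 7.2.4 is a minimum list and puts the pregnancy test in the same numbered item as the routine urine test. The synopsis and 5.1.1 call for laboratory tests at Visit 4, and 7.4.3 gives 7.2 the same standing as 7.1. A site could reasonably perform the whole item. On that reading the fault is an inconsistency between 7.1 and 7.2.4 rather than an absent test. This reading is available but not compelled, and two readings of a safety test are themselves a reason to settle the text.

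A second argument is that the screening test serves eligibility. Section 7.3.1 ties no pregnancy test to the PET, so omitting it at the last visit breaks no stated rule. That is correct: this is a gap in the schedule, not a contradiction. The effect of the screening order is still that the first exposure follows a test and the second need not.

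Third, there are other safeguards. Contraception is required at entry, and subjects are asked about changes in their condition at each visit (7.4.1.2). An exclusion criterion arising during the trial can lead to withdrawal, and pregnancy must do so (5.5.2, 5.5.1). Section 7.4.2 requires immediate discontinuation of the drug and follow-up. These narrow the risk considerably, but they act on a pregnancy or a lapse that somebody knows about.

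Two smaller points stand. Section 5.4 concerns the start of treatment and adds little about a PET twelve weeks later. The consequence also cannot be sized, because the number of women of child-bearing potential and the fetal dose are not given.

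**Conclusion.** The point holds. Followed as written, 7.1 allows the second tracer and CT exposure on a pregnancy test 81 to 101 days old, where the first PET has one at most 14 days old. The tracer part of that exposure is about 3 to 6 mSv to the mother.

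This rests on 7.1 being read as the operative schedule; a site that performs all of 7.2.4 at Visit 4 would already be covered. It also rests on some participants being of child-bearing potential. The protocol does not say how many, and the number could be anywhere from 0 to all 20. The remaining risk is limited to a conception during treatment that is still unrecognised at Visit 4. The correction should be made because it is cheap and concerns safety; the efficacy analysis does not change.

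**What to change.** In 7.1, Visit 4 item h), add a urine pregnancy test for women of child-bearing potential, with the result available before the PET. In 7.2.4, state that this test is done at screening and at Visit 4. A matching row in Appendix I would help but is optional.

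The cost is one phrase in each section and one dipstick per woman of child-bearing potential, 0 to 20 in all, on urine already collected at Visit 4. The sample must be taken and read before tracer is given. A false positive would delay that PET until a repeat test, either within the ±3-day window or as a recorded deviation. The change protects the second PET only; it does not detect pregnancy earlier in treatment.
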